3.5.2. Laboratory Data

Safety laboratory tests will be performed as described in the protocol.

For PART-1, PART-3 and PART-5, baseline will be the last pre-dose measurement prior to administration of PF-07321332 in each study period. For PART-2, baseline will be the last pre-dose measurement. For PART-4, baseline will be the last pre-dose measurement prior to administration of PF-07321332.

For PART-5, the pre-dose (Day -1) sample in Period 2 will also be used as a Day 5 (96h) sample.

To determine if there are any clinically significant laboratory abnormalities, the hematological, clinical chemistry (serum) and urinalysis safety tests will be assessed against the criteria specified in the sponsor reporting standards. The assessment will take into account whether each participant's baseline test result is within or outside the laboratory reference range for the particular laboratory parameter.

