| Drug screen testing  | X              | $X^{d}$   |   |               |               |               |               |               |               |               |               |                  |               |          |          |          |          |       |                               |     |
| Urinalysis   | X              | X         |   |               |               |               |               |               |               | X             |               |                  |               | X        | X        | X        |          |       |                               | X   |
|  F-NMR Measurement and metabolic profiling n,p |                | X         | X | $\rightarrow$    | $\rightarrow$ | X        | X        | X        | X        | X     |                               |     |
| Feces Collection for:  |                |           |   |               |               |               |               |               |               |               |               |                  |               |          |          |          |          |       |                               |     |
|  F-NMR Measurement and metabolic profiling o,p |                | X         | X | $\rightarrow$    | $\rightarrow$ | X        | X        | X        | X        | X     |                               |     |

- a. **Visit Identifier:** Day relative to start of study treatment (Day 1).
- b. **Period 1 to Period 4:** Washout duration of at least 5 days between dosing. May be adjusted based on emerging data. Period 3 and 4 are optional.
- c. F/U Contact: Follow-up phone call may occur via telephone 28-35 days after the last dose of investigational product in the final period.
- d. Period 1 only. If participants are discharged and readmitted, follow all Period 1 activities except I/E criteria, medical history update

- e. SARS-CoV-2 RT-PCR: Screening, admission (Day -1), 4 days following admission (Day 4), ad hoc test based on symptoms, and for ambulatory on-site visits.
- f. CRU Confinement: Participants will be required to stay at CRU from Day -1 in Period 1 until completing Day 4 (72h) activities in the final period.

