| Drug screen testing                      | X                 | X d |                          |                             |   |   |   |   |   |   |   |   |    |     |       |                               |       |         |              |   |
| Urinalysis                               | X                 | X d |                          |                             |   |   |   |   |   |   |   |   |    |     | С     |                               | X     | $X^{i}$ |              | X |

- a. **Visit Identifier:** Day relative to start of study treatment (Day 1).
- b. Period 1 to Period 4: Washout duration of at least 5 days between 1st dosing in each period. Periods 3 and 4 are optional.
- c. F/U Contact: Follow-up phone call may occur via telephone 28 to 35 days after the last dose of investigational product in the final period.
- d. Period 1 only. If participants are discharged and readmitted, follow all Period 1 activities except I/E criteria, medical history update
- e. **SARS-CoV-2 RT-PCR:** Screening, admission (Day -1), 4 days following admission (Day 4), ad hoc test based on symptoms, and for ambulatory on-site visits.
- f. CRU Confinement: Participants will be required to stay at CRU from Day -1 in Period 1 until completing Day 5 (96h) activities in the final period.
- g. **Physical Examination:** Complete physical examination will be conducted at Screening or upon admission (Day -1) in Period 1. Brief physical examination may be performed at other times, as appropriate, for findings during previous examination or new/open AEs, at investigator's discretion.
- h. **Continuous cardiac telemetry monitoring:** Baseline telemetry to be recorded for at least 2 hours between admission and prior to dosing while awake. Post dose telemetry will continue for 12 hours after the start of dosing for each period.
- i. Last Period only, unless discharged at the discretion of the investigator.
- j. **Ritonavir:** To be administered approximately 12 hours before PF-07321332 administration on Day 1.
- k. HBsAb: Can be done either automatically or only if HBcAb or HBsAg is positive, as per local practices.

- m. Study Drug Administration: The first split dosing of study drug should be at approximately 2h after the breakfast.
- n. COVID-19 Assessment: Temperature check as per local requirement. Questionnaire before admission.

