#### PART-1: SAD

The crossover design will permit both a within and between participant assessment of safety, tolerability, and PK. Furthermore, 2 interleaving cohorts will permit assessment of safety and PK over a wider dose range within a given participant compared to a sequential cohort design. To permit an unbiased assessment of safety, the administration of active versus placebo in each period will be double blinded to site staff (except those involved in preparation of doses) as well as the study participants.

For a given participant, dosing will be separated by  $\geq 5$  days. This planned dosing interval is deemed sufficient to permit washout of previous treatment. Based on the projected PF-07321332 effective  $t_{\frac{1}{2}}$  of  $\sim 2$  hours (see Section 2.2.1.4), almost complete PK washout is expected within 24 hours of dosing.

In SAD period, the urine and feces may be collected to calculate total excretion of drug-related material using F-NMR technique and understand metabolic profile as described in previous publications.

If a reasonable dose of PF-07321332 is not able to achieve desired concentrations in the efficacious range, ritonavir may be used as PK boosting agent. If required, 3 doses of 100 mg ritonavir at -12h, 0h (co-administered with PF-07321332) and 12h may be used as boosting agent to increase the exposure of PF-07321332 because the primary route of elimination of PF-07321332 is expected to be via CYP3A4 mediated metabolism. This dose of ritonavir is a subtherapeutic dose and provides maximum CYP3A4 inhibition. In SAD, participants will begin receiving ritonavir dose approximately 12 hours before the PF-07321332 dose to maximize the PK boosting potential of ritonavir. Although ritonavir is generally recommended to be dosed under fed condition for better gastrointestinal tolerability, lower dose of ritonavir (100 mg) is expected to provide acceptable gastrointestinal tolerability based on the fact that lopinavir/ritonavir combination are recommended to be dosed with or without food.

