### **Potential Cases of Acute Kidney Injury**

Abnormal values in SCr concurrent with presence or absence of increase in BUN that meet the criteria below, in the absence of other causes of kidney injury, are considered potential cases of acute kidney injury and should be considered important medical events.

An increase of  $\geq 0.3$  mg/dL (or  $\geq 26.5$  µmol/L) in SCr level relative to the participant's own baseline measurement should trigger another assessment of SCr as soon as practically feasible, preferably within 48 hours from awareness.

If the second assessment (after the first observations of  $\geq$ 0.3 mg/dL [or  $\geq$ 26.5  $\mu$ mol/L] in SCr relative to the participant's own baseline measurement) is  $\geq$ 0.4 mg/dL (or  $\geq$ 35.4  $\mu$ mol/L), the participant should be discontinued from the study and adequate, immediate, supportive measures taken to correct apparent acute kidney injury.

Participants should return to the investigator site and be evaluated as soon as possible, preferably within 48 hours from awareness of the second assessment confirming abnormal SCr result. This evaluation should include laboratory tests, detailed history, and physical assessment. In addition to repeating SCr, laboratory tests should include serum BUN, serum creatine kinase, and serum electrolytes (including at a minimum potassium, sodium,

phosphate/phosphorus, and calcium), in addition to urinary dipstick, urine microscopic examination, and urinary indices. All cases confirmed on repeat testing as meeting the laboratory criteria for acute kidney injury, with no other cause(s) of laboratory abnormalities identified, should be considered potential cases of drug-induced kidney injury irrespective of availability of all the results of the investigations performed to determine etiology of the abnormal SCr. If  $\geq$ 2 healthy participants in a given period in PART-1 and 3 and in a treatment arm in PART-2 are noted to have 2 consecutive SCr results of  $\geq$ 0.3 mg/dL (or  $\geq$ 26.5 µmol/L), an assessment of whether the finding may be considered an adverse drug reaction should be undertaken.

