# 10.6. Appendix 6: Liver Safety: Suggested Actions and Follow-up Assessments Potential Cases of Drug-Induced Liver Injury

Humans exposed to a drug who show no sign of liver injury (as determined by elevations in transaminases) are termed "tolerators," while those who show transient liver injury, but adapt are termed "adaptors." In some participants, transaminase elevations are a harbinger of a more serious potential outcome. These participants fail to adapt and therefore are "susceptible" to progressive and serious liver injury, commonly referred to as DILI. Participants who experience a transaminase elevation above 3 × ULN should be monitored more frequently to determine if they are an "adaptor" or are "susceptible."

In the majority of DILI cases, elevations in AST and/or ALT precede TBili elevations (>2 × ULN) by several days or weeks. The increase in TBili typically occurs while AST/ALT is/are still elevated above 3 × ULN (ie, AST/ALT and TBili values will be elevated within the same laboratory sample). In rare instances, by the time TBili elevations are detected, AST/ALT values might have decreased. This occurrence is still regarded as a potential DILI. Therefore, abnormal elevations in either AST OR ALT in addition to TBili that meet the criteria outlined below are considered potential DILI (assessed per Hy's law criteria) cases and should always be considered important medical events, even before all other possible causes of liver injury have been excluded.

The threshold of laboratory abnormalities for a potential DILI case depends on the participant's individual baseline values and underlying conditions. Participants who present with the following laboratory abnormalities should be evaluated further as potential DILI (Hy's law) cases to definitively determine the etiology of the abnormal laboratory values:

- Participants with AST/ALT and TBili baseline values within the normal range who subsequently present with AST OR ALT values >3 × ULN AND a TBili value >2 × ULN with no evidence of hemolysis and an alkaline phosphatase value <2 × ULN or not available.
- For participants with baseline AST **OR** ALT **OR** TBili values above the ULN, the following threshold values are used in the definition mentioned above, as needed, depending on which values are above the ULN at baseline:
  - Preexisting AST or ALT baseline values above the normal range: AST or ALT values >2 times the baseline values AND >3 × ULN; or >8 × ULN (whichever is smaller).

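### SAP 3.5.2 takes a new laboratory baseline in each period of PART-1 and PART-5 and plans no assessment against the value before the first dose, so summaries can understate a persistent drug-related abnormality

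*SAP*

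**What the plan says.** SAP 3.5.2 states for PART-1, PART-3 and PART-5 that "baseline will be the last pre-dose measurement prior to administration of PF-07321332 in each study period". On abnormal values it adds: "The assessment will take into account whether each participant's baseline test result is within or outside the laboratory reference range". The criteria themselves are left to the sponsor reporting standards. SAP 6.6.2 plans listings and by-treatment summaries under the same standards. Neither section defines a summary against the value before the first dose.

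The minimum interval in PART-1 is in protocol section 1.3, Table 1, footnote b: "Washout duration of at least 5 days between dosing". For PART-5 it is in footnote b of the PART-5 schedule (Table 6 of section 1.3): "Washout duration of at least 5 days between 1st dosing in each period". In both schedules the Day -1 safety laboratory entry lacks the Period-1-only footnote that other Day -1 entries carry, so it applies to every period.

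SAP 3.5.2 has one rule linking a Day -1 sample to the preceding period: "For PART-5, the pre-dose (Day -1) sample in Period 2 will also be used as a Day 5 (96h) sample". It does not cover PART-1, or Periods 3 and 4 of PART-5.

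**The concern.** The washout is justified by pharmacokinetics. Protocol 4.2 says for PART-1 that "almost complete PK washout is expected within 24 hours of dosing", and for PART-5 it cites half-life and inter-individual variability. Clearance of the drug does not show that a laboratory effect has resolved. Protocol Appendix 6 notes that in most drug-induced liver injury cases "elevations in AST and/or ALT precede TBili elevations (>2 × ULN) by several days or weeks". That describes the lag between two liver tests, not recovery after a single dose. It does show that liver findings can evolve on a longer scale than the gap between periods.

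PART-1 re-doses the same people, partly at rising doses. If an effect is still present on the next Day -1, that value becomes the reference for the next period, and its position inside or outside the reference range affects how later values are judged. At stake is the summary of abnormal laboratory findings, which belongs to the primary endpoint of both parts, with about 4 active participants per dose level in PART-1.

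**Working it through.** **Step 1: timing of the baseline.** Inputs: a minimum interval of 5 days (schedules in protocol 1.3), with Day -1 the day before the next dose.

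5 × 24 h − 24 h = 96 h after the previous period's first dose.

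This reproduces the SAP's own label for the PART-5 Period 2 sample, Day 5 (96h). With dosing at 08:00, the Day -1 calendar day runs from 120 − 32 = 88 h to 120 − 8 = 112 h, hence about 96 h. The interval may be longer, and the PART-1 washout may be adjusted. SAP 2.2.6 can be read as placing PART-5 baseline safety laboratory tests before breakfast on Day 1. The schedule and SAP 3.5.2 say Day -1, which is used here.

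**Step 2: where each laboratory sample is counted.**

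| Sample | Post-dose value of the preceding dose? | Baseline of the next period? |
|---|---|---|
| PART-1, 6, 24, 48, 72 h | Yes | No |
| PART-1, Day -1 of Periods 2 to 4 | No rule | Yes |
| PART-5, 24 h | Yes | No |
| PART-5, Day -1 of Period 2 | Yes (SAP 3.5.2) | Yes |
| PART-5, Day -1 of Periods 3 and 4, if run | No rule | Yes |

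In PART-1, a change that first appears between 72 h and about 96 h is attributed to no dose, yet becomes the next baseline.

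**Step 3: how often a PART-1 baseline follows active drug.** Input: the provisional dosing scheme in protocol 4.1 (also headed Table 6), 2 participants per row, all four periods run.

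| Row | Periods 1 to 4 | Active periods | Later baselines directly after active | Later baselines after any active |
|---|---|---|---|---|
| Cohort 1, a | PL, D3, D5, D3 tablet | 3 | 2 | 2 |
| Cohort 1, b | D1, PL, D5, PL | 2 | 2 | 3 |
| Cohort 1, c | D1, D3, PL, D3 tablet | 3 | 2 | 3 |
| Cohort 2, a | PL, D4, D6, PL | 2 | 2 | 2 |
| Cohort 2, b | D2, PL, D6, D2 fed | 3 | 2 | 3 |
| Cohort 2, c | D2, D4, PL, D2 fed | 3 | 2 | 3 |

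- Later baselines: 6 rows × 3 × 2 participants = 36.
- Directly after an active period: 12 × 2 = 24 of 36.
- After any earlier active dose: 16 × 2 = 32 of 36.
- Directly between an active dose and a higher active dose: 4 rows × 1 × 2 = 8 of 36.
- If only Periods 1 and 2 run: 8 of 12 Period 2 baselines follow active drug.

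**Step 4: illustration of size.** Assumption: creatinine rises by s mg/dL in each active period and does not recover. With k active periods, the rise from the value before the first dose is k × s, and the rise from the period baseline is s in each active period. The scheme gives k = 2 or 3.

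| s (mg/dL) | From period baseline | From pre-first-dose value, k = 2 | k = 3 |
|---|---|---|---|
| 0.10 | 0.10 | 0.20 | 0.30 |
| 0.15 | 0.15 | 0.30 | 0.45 |
| 0.20 | 0.20 | 0.40 | 0.60 |

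With Periods 1 and 2 only, k is at most 2, so s = 0.15 gives at most 0.30. If each rise resolves before the next Day -1, both references give the same value. The step sizes are assumptions; the documents give no laboratory results.

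**The case against.** A period-specific baseline is a usual crossover choice and matches the vital sign and ECG rules in SAP 3.5.3 and 3.5.4. The study is descriptive, with no hypothesis tests. Clinically significant values are repeated until resolved (protocol 8.2.4), reportable changes become adverse events, treatment-emergent events are anchored to the first dose (SAP 3.5.1), and all laboratory data are listed. All of this stands. It means that detection is protected and that the baseline rule is not itself an error.

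Three stronger readings are tempting and not supported.

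- **Such abnormalities vanish from the summaries.** Values seen within a period are counted there, and the PART-5 Period 2 Day -1 value also counts as a Period 1 value. The SAP says baseline status is taken into account, not that abnormal-baseline values are excluded. It names change-from-baseline endpoints for vital signs and ECG, not for laboratory data.
- **The effect builds over four rising doses, 4 × 0.15 = 0.60 mg/dL.** The provisional PART-1 scheme gives every participant at least one placebo period, so 0.45 is the ceiling for that step, and Period 4 does not continue the rise. In PART-5, placebo separates the active periods. A Treatment Q baseline falls at least 2 × 5 × 24 − 24 = 216 h (9 days) after the first dose of Treatment P.
- **The SAP rule shifts the protocol's kidney and liver triggers.** Protocol 7.1 says an increase of at least 0.3 mg/dL "in SCr level relative to the participant's own baseline measurement should trigger another assessment of SCr", and Appendix 6 refers to pre-existing values. Neither adopts the SAP's period baseline, and the Appendix 6 case definition also needs a bilirubin criterion.

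**Conclusion.** The point holds as a gap in the summaries, mainly in PART-1. A Day -1 value affected by an earlier dose can be classed as an abnormal baseline, with no rule assigning it to that dose and no planned comparison with the value before the first dose. Under the provisional scheme with all periods run, 24 of 36 later PART-1 baselines directly follow active drug, so the situation is common by design. Whether any abnormality is understated depends on effects lasting beyond about 4 days and on the sponsor standards, neither of which the documents settle. The 0.30 to 0.45 against 0.15 mg/dL contrast shows what a supplementary reference could reveal; it is not a predicted error. The loss is in the summary tables, not in detection. This is a worthwhile improvement at low cost rather than a flaw that threatens the study.

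PART-3 uses the same baseline rule but is not a dose escalation. Its Day -1 footnote is missing from the text available, so it was not assessed.

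**What to change.** Keep the period baseline for by-period summaries. Add to SAP 3.5.2 and 6.6.2 one supportive summary for PART-1 and PART-5. It would assess abnormalities and maximum changes in ALT, AST, total bilirubin, creatinine and the coagulation tests, across all periods, against the last value before the first dose of study intervention in that part. In that table, count each later-period Day -1 value as a post-dose value of the preceding period, not as a pre-existing abnormality.

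The cost is a few SAP sentences and one table from data already collected. The downside is that a carried-over change cannot be tied to a single dose, so the table is supportive only.

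Separately, protocol 7.1 and Appendix 6 do not say which period's baseline applies. Those passages should be reconciled with SAP 3.5.2. No clinical rule is proposed here.

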3.5.3. Vital Signs

Single supine blood pressure, respiratory rate, temperature and pulse measurements will be taken at times detailed in the SoA given in the protocol.

For PART-1, PART-3 and PART-5, baseline will be defined as the last pre-dose measurement prior to administration of PF-07321332 in each study period. For PART-2, baseline will be the last pre-dose measurement. For PART-4, baseline will be the last pre-dose measurement prior to administration of PF-07321332.

The following vital signs endpoints will be determined:

- Change from baseline in supine systolic and diastolic blood pressure, pulse rate, temperature and respiratory rate.

- The maximum decrease from baseline over all measurements taken post-dose for supine systolic and diastolic blood pressures and respiratory rate.
- The maximum increase from baseline over all measurements taken post-dose for supine pulse rate and temperature.

The maximum increase from baseline will be calculated by first subtracting the baseline value from each post-dose measurement to give the change from baseline. The maximum of these values over the respective period will then be selected, except in the case where a participant does not show an increase. In such an instance, the minimum decrease should be taken.

Similarly, the maximum decrease from baseline will be determined by selecting the minimum value of the changes from baseline. In cases where a participant does not show a decrease, the minimum increase should be taken.

3.5.4. ECG

A 12-lead ECG will be obtained on all participants at screening. A triplicate measurement will be performed in PART-1, PART-2 and PART-5, and a single measurement in PART-3 and PART-4.

12-lead ECGs will be recorded on all participants at times detailed in the SoA given in the protocol. Triplicate measurements will be performed in PART-1, PART-2 and PART-5, and single measurements in PART-3 and PART-4. The QT, heart rate, QTcF, PR and QRS will be recorded at each assessment time.

The average of the triplicate readings collected at each assessment time will be calculated for each ECG parameter. For PART-1 and PART-5, baseline will be defined as the average of the triplicate measurements prior to administration of PF-07321332 in each study period. For PART-2, baseline will be defined as the average of the triplicate measurements prior to administration of PF-07321332 on Day 1. For PART-3, baseline will be defined the last measurement prior to administration of PF-07321332 in each study period. For PART-4, baseline will be defined as the last measurement prior to administration of PF-07321332.

The following ECG endpoints will be determined:

- Change from baseline in QT interval, heart rate, QTcF interval, PR interval, and QRS complex.
- The maximum absolute value (post-dose) will be calculated for QTcF, PR and QRS.
- The maximum increase from baseline over all measurements taken post-dose will be calculated for QTcF.

The maximum increase from baseline will be calculated by first subtracting the baseline value from each triplicate-average post-dose measurement to give the change from baseline. The

maximum of these values over the respective period will then be selected, except in the case where a participant does not show an increase. In such an instance, the minimum decrease should be taken.

CCI

